### **Summary of GPA/MPA Eligibility Criteria**

Data from the electronic health record will be used to determine diagnosis of GPA or MPA, and will be based on fulfillment of the American College of Rheumatology (ACR)/European Alliance of Associations for Rheumatology (EULAR) Classification Criteria, or the Chapel Hill Consensus Criteria and/or clinician-documented diagnosis and management as GPA or MPA (see Appendices D and E and Pyo et al. 2023).

#### Analysis 1

1. Diagnosed with new or relapsing GPA or MPA on or after December 1, 2021, the first date of avacopan use at Mass General Brigham
2. At least 18 years old on index date

#### Analysis 2

1. Diagnosed with new or relapsing GPA or MPA on or after December 1, 2021, the first date of avacopan use at Mass General Brigham

2. At least 18 years old on index date
3. Prescribed avacopan

#### Analysis 3

1. Diagnosed with new or relapsing GPA or MPA on or after December 1, 2021, the first date of avacopan use at Mass General Brigham
2. At least 18 years old on index date
3. Initiated avacopan

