**Analysis 2: Initiated Avacopan and Did Not Initiate Avacopan**

[figure not shown]
Baseline (12 Month Lookback from Index Date)

- Demographics
- Clinical Characteristics
- Other GPA/MPA Medication Exposures
- Healthcare Resource Utilization and Costs

Index date          Date of avacopan prescription (for both avacopan initiators and non-initiators)
	

Inclusion criteria
 
 
• Diagnosed with new or relapsing GPA or MPA on or after December 1, 2021, the first date of avacopan use at Mass General Brigham
 
• At least 18 years old on index date
 
• Prescribed avacopan
 
	
Characteristics to be evaluated
 
 
• Demographic features (e.g., age, sex, race/ethnicity)
 
• GPA/MPA features (e.g., BVAS v3, organ involvement, new or relapsing disease)
 
• Comorbidities at index date (e.g., hypertension, hyperlipidemia, Charlson Comorbidity Index)
 
• Healthcare resource utilization up to 12 months prior to index date
 
• Reason for not initiating avacopan
 

Exclusion criteria
 
 
• A diagnosis of EGPA.
 
• GPA/MPA attributed to cocaine/levamisole.
 
• No treatment of GPA/MPA during the baseline or follow-up periods (i.e., not treated for their GPA/MPA).
 
	

Index date Date of avacopan initiation
	
Primary outcomes to be evaluated
 
 
• Proportion achieving discontinuation of glucocorticoids for treatment of GPA or MPA 1 month before Month 6 and disease remission within 6 months of avacopan initiation.
 
• Proportion achieving sustained remission at Month 12, defined as remission at Month 6 and remission at Month 12, with no glucocorticoid treatment for GPA/MPA 1 month before Month 12, and no relapse between Months 6 and 12
 

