
Inclusion criteria
 
 
• Diagnosed with new or relapsing GPA or MPA on or after December 1, 2021, the first date of avacopan use at Mass General Brigham
 
• At least 18 years old on index date
 
• Prescribed avacopan
 
 
Exclusion criteria
 
 
• A diagnosis of EGPA.
 
• GPA/MPA attributed to cocaine/levamisole.
 
• No treatment of GPA/MPA during the baseline or follow-up periods (i.e., not treated for their GPA/MPA).
 
	
Additional endpoints to be evaluated
 
 
• Glucocorticoid exposure, glucocorticoid toxicity
 
• Disease activity, renal outcomes, ANCA titer changes
 
• Change in comorbidities/biomarkers (e.g., BMI, lipids, A1c)
 
• Healthcare resource utilization (analysis from MGH only)
 
• Patient reported outcome measures
 
• Adverse events attributed to avacopan, infection, relapse, mortality
 

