Among patients who use avacopan, to describe the outcomes, including disease- and treatment-specific outcomes	
 
• Complete remission at Month 6
 
• Complete remission at Month 12
 
• Proportion who achieve discontinuation of glucocorticoids for treatment of GPA or MPA 1 month before Month 6 and disease remission (based on a BVAS v3 of 0) within 6 months of avacopan initiation, as defined in ADVOCATE
 
• Proportion who achieve sustained remission at Month 12.
 
• Cumulative glucocorticoid exposure
 
• Median daily glucocorticoid dose
 
• Glucocorticoid toxicity
 
• Glucocorticoid Toxicity Index – Metabolic Domain (GTI-MD)
 
• Change in A1c
 
• Change in BMI
 
• Change in lipids
 
• Renal parameters (estimated glomerular filtration rate [eGFR], proteinuria, hematuria)
 
• ANCA titers
 
• Pathology results
 
• Adverse Events
 
• Patient reported outcome measures (RAPID-3, mHAQ, PHQ-8, GAD-7, and PROMIS)
 

Secondary	
To investigate baseline factors associated with glucocorticoid discontinuation and relapse risk in patients who initiate avacopan	Descriptive analysis of baseline demographic and clinical characteristics 
 
• Demographic features (e.g., age, sex, race/ethnicity)
 

	
 
GPA/MPA features (e.g., BVAS v3, organ involvement, new or relapsing disease)
 
Comorbidities at index date (e.g., hypertension, hyperlipidemia, Charlson Comorbidity Index)
 
Healthcare resource utilization up to 12 months prior to index date
 

To evaluate the association of glucocorticoid use patterns with relapse risk in patients who initiate avacopan	
Relapse, defined as a return (after prior improvement) of vasculitis activity on the basis of at least one major BVAS/WG item, at least three minor BVAS v3 items, or one or two minor BVAS v3 items for at least two consecutive clinical visits (ADVOCATE definition). Relapses will be assessed after Month 1.
 
Patients who had an increase in the BVAS v3 of <3 and the absence of major BVAS/WG items define a minor relapse. All other patients are defined as a major relapse. (Miloslavsky et al. 2015)

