#### **Follow-up**

Analysis 1: Comparing baseline features among those prescribed and those not prescribed avacopan

Index Date

- Date of avacopan prescription or date of non-avacopan, non-glucocorticoid treatment prescription (Appendix C, immunosuppressive drugs)

Follow-Up Date

- There is no follow-up period, as this analysis is examining baseline factors

Analysis 2: Comparing baseline features among those initiating and those not initiating avacopan after prescription

Index Date

- Date of avacopan prescription (for both avacopan initiators and non-initiators)

Analysis 3: Month 1, 3, 6, and 12 outcomes among patients who initiate avacopan

Index Date

- Date of avacopan initiation

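### Analysis 3 requires neither active disease nor glucocorticoid use at avacopan initiation, so patients already in remission or off glucocorticoid raise the primary proportions and distort time to discontinuation

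*Protocol*

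**What the plan says.** The Protocol's Summary of GPA/MPA Eligibility Criteria gives three conditions for Analysis 3: "Diagnosed with new or relapsing GPA or MPA on or after December 1, 2021, the first date of avacopan use at Mass General Brigham", adult age on the index date, and "Initiated avacopan". The Analysis 3 box of the Study Design Schema repeats the first two but has "Prescribed avacopan" as the third. It adds exclusions for EGPA, for drug-attributed disease and for patients who received no treatment at all. The index date in the Follow-up section is "Date of avacopan initiation".

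The first primary outcome in the schema is "Proportion achieving discontinuation of glucocorticoids for treatment of GPA or MPA 1 month before Month 6 and disease remission within 6 months of avacopan initiation". The endpoint table under Research Question and Objective(s) specifies "disease remission (based on a BVAS v3 of 0) within 6 months of avacopan initiation, as defined in ADVOCATE". The second primary outcome is sustained remission: remission at both Month 6 and Month 12, no relapse between them, and no glucocorticoid for the disease in the month before Month 12.

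The Follow-Up Dates section measures glucocorticoid discontinuation as a time from initiation. Data Analysis plans Kaplan-Meier and Cox analyses of it.

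**The concern.** The disease criterion refers to an episode at any time since December 2021, while the clock starts when avacopan starts. The two can be far apart. A patient treated by other means in 2022, brought to BVAS 0 and started on avacopan in 2023 satisfies every listed condition.

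The primary proportions are meant to show what happens to disease activity and glucocorticoid use after avacopan begins. A patient who has neither activity nor glucocorticoid to lose cannot inform that question, yet is counted as a success by staying unchanged. The study is descriptive, so these proportions are its main product. The endpoint table also says that the Month 6 definition comes from the reference trial, which invites readers to set the figures side by side. Study Background and Rationale describes that trial as one of inducing and sustaining remission in new or relapsing disease.

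**Working it through.** The protocol states no figure for the affected share and has no power calculation, so there is nothing to reproduce. The check has three parts.

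**1. What can be met on day 0.** Take a patient with BVAS 0 and no glucocorticoid at initiation.

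- *Remission part of the Month 6 outcome.* As worded it may be met at any time within 6 months, so it is met on day 0.
- *Glucocorticoid part of the Month 6 outcome.* This is a status in the month before Month 6. It cannot be scored on day 0, but the patient meets it by staying off. Discontinuation after initiation is undefined for this patient.
- *Sustained remission.* This needs status at Month 6 and Month 12. It cannot be scored on day 0; the patient has only to maintain status.
- *Time to glucocorticoid discontinuation.* The stop date precedes time zero, so the time is zero, negative or undefined.

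Study Background and Rationale describes the reference endpoint as remission at Month 6, and Variables also lists remission at Month 6. Scoring it that way removes the day-0 success but not the inflation from patients who merely stay in remission.

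**2. Size for the proportions (illustration; the inputs are assumptions).** Let f be the share of initiators already at BVAS 0 and off glucocorticoid, q their chance of meeting the endpoint, and p the proportion among the others.

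Observed proportion = f·q + (1 − f)·p, so inflation = f·(q − p).

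One value of p, 66%, is the reference trial's sustained-remission rate quoted in the protocol, used only as an illustrative rate. The other p values, f and q have no source in the documents. With q = 0.90:

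| f | p = 50% | p = 66% |
|---|---|---|
| 10% | 54.0% (+4.0) | 68.4% (+2.4) |
| 20% | 58.0% (+8.0) | 70.8% (+4.8) |
| 30% | 62.0% (+12.0) | 73.2% (+7.2) |

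Over f = 0 to 30%, q = 0.8 to 1.0 and p = 40 to 66%, the smallest inflation is 0 (f = 0). The largest is 0.30 × (1.00 − 0.40) = 18 points. For scale, the 95% half-width with 112 initiators at 50% is 1.96 × √(0.5 × 0.5 / 112) = 9.3 points.

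**3. Effect on time to discontinuation.** Suppose a share g is off glucocorticoid at initiation and is scored as an event at time zero. The pooled curve is then (1 − g) times the curve of patients actually on glucocorticoid. The pooled median falls where the latter curve equals 0.5 / (1 − g):

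- g = 10%: 0.5 / 0.9 = 0.556, so only 44.4% of patients on glucocorticoid have stopped;
- g = 20%: 0.5 / 0.8 = 0.625, so 37.5%;
- g = 30%: 0.5 / 0.7 = 0.714, so 28.6%.

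The reported median would then be too early for the patients who had something to discontinue. In the Cox model, time-zero events would attribute to baseline factors a stop that came before avacopan.

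**The case against.** Five points are made on the other side.

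- *The title claim can be overdrawn.* A reader might infer that the primary outcomes as a whole can be met on day 0. The documents do not support that: only the BVAS part of the Month 6 outcome can. This stands, and the point is limited accordingly.
- *The denominator.* A reader might infer from the schema's entry wording that 133 prescribed patients, not 112 initiators, form the denominator; 74 successes would be 66.1% of 112 but 55.6% of 133. That does not arise. The 133 − 112 = 21 patients not counted as initiators have no initiation date on record, hence no Month 6 or Month 12, and Follow-up and Variables both confine Analysis 3 to initiators. The schema wording is an editorial slip.
- *The indication.* Variables describes the Analysis 1 exposure as prescription for new or relapsing disease, which suggests that avacopan was given for an episode. That supports the intended indication, but it fixes neither disease activity nor glucocorticoid use on the initiation date. The feasibility remark that most patients stopped glucocorticoid within 2 months of initiation suggests many were taking it, but gives no count of those already off.
- *Redaction.* The visible list is a summary in the abstract and later sections are withheld, so a fuller criterion may exist there. This stands as a limit on certainty, although two separate visible lists both lack it.
- *Legitimate target and analysis-plan detail.* Describing all real-world initiators is a fair aim, and outcomes are not hypothesis-tested. This is why all initiators should stay in. But eligibility, time zero and endpoint wording are set in this document, and their combination causes the problem.

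**Conclusion.** The point holds in a limited form. As the visible text stands, Analysis 3 counts patients already at BVAS 0 toward remission and patients already off glucocorticoid toward discontinuation, and gives the latter no meaningful time to discontinuation. Both primary proportions are inflated if such patients meet the endpoints more often than the rest.

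The amount cannot be computed from the documents. The range of 0 to about 18 points rests on assumed shares of 0 to 30% and assumed success rates; if no such patients exist, the effect is nil. The illustration covers only patients who meet both conditions at initiation; those who meet one have one component left to achieve.

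A reader might go further and make patients with BVAS v3 above 0 the sole primary population. The documents do not compel that, since a description of all initiators is within the stated aim.

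**What to change.** - Keep all initiators in Analysis 3. Report the Month 6 and Month 12 remission outcomes separately for patients with BVAS v3 above 0 and with BVAS v3 of 0 at initiation, and interpret only the former as remission achieved after avacopan.
- Restrict time to glucocorticoid discontinuation, and its Cox model, to patients taking glucocorticoid for GPA/MPA at initiation. State how many are left out.
- Score Month 6 remission as status at Month 6, in line with Study Background and Rationale and with Variables.
- In the Analysis 3 box of the schema, replace the prescription criterion with the initiation criterion of the eligibility summary.

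Baseline BVAS v3 and the dates and patterns of glucocorticoid use are already listed for collection, so the change needs wording and stratified tables but no new data. The cost is a smaller denominator, hence wider intervals, for the stratified remission figures and the discontinuation analyses.

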#### **Follow-up**

Analysis 1: Comparing baseline features among those prescribed and those not prescribed avacopan

Index Date

- Date of avacopan prescription or date of non-avacopan, non-glucocorticoid treatment prescription (Appendix C, immunosuppressive drugs)

Follow-Up Date

- There is no follow-up period, as this analysis is examining baseline factors

Analysis 2: Comparing baseline features among those initiating and those not initiating avacopan after prescription

Index Date

- Date of avacopan prescription (for both avacopan initiators and non-initiators)

Analysis 3: Month 1, 3, 6, and 12 outcomes among patients who initiate avacopan

Index Date

- Date of avacopan initiation

## Follow-Up Dates (vary by analysis/outcome)

### Treatment Outcomes

- Date of avacopan discontinuation (for time from initiation to discontinuation)
- Date of glucocorticoid discontinuation and usage patterns, including dosage changes (for time from initiation to discontinuation)
- 6 months after avacopan initiation (for primary outcomes at Month 6)
- 12 months after avacopan initiation (for primary outcomes at Month 12)

### Clinical Outcomes

- Date of relapse (any and stratified by major or minor), (for time from initiation to relapse)
- Date of death (for time from initiation to death)
- Date of end of follow-up (for time from initiation to outcomes of interest)
- Date of loss to follow-up (for time from initiation to outcomes of interest)
- Date of adverse event or other event of interest in specific analyses (for time from initiation to adverse event)

## Variables

The exposures of interest include:

- Analysis 1: Prescription and non-prescription of avacopan for newly diagnosed or relapsing GPA/MPA;
- Analysis 2: Initiation and non-initiation of avacopan among those prescribed avacopan;
- Analysis 3: Patients who initiate avacopan.

The outcomes of interest include:

- Analysis 1: Comparing baseline features among those prescribed and those not prescribed avacopan
- Analysis 2: Comparing baseline features of patients initiating and not initiating avacopan among those prescribed avacopan.
  - Features compared in Analysis 1 and 2, include: 1) Demographic features (e.g., age, sex, race/ethnicity); 2) GPA/MPA features (e.g., BVAS v3, organ involvement, new or relapsing disease); 3) Comorbidities at index date (e.g., hypertension, hyperlipidemia, Charlson Comorbidity Index); 4)

Healthcare resource utilization up to 12 months prior to index date; 5) reason for not initiating (Analysis 2 only)

- Analysis 3: outcomes among those who initiate avacopan, including:
  - 1) Glucocorticoid exposure; 2) Remission at Month 6 (BVAS v3 = 0); 3) Sustained remission at Month 12; 4) Glucocorticoid toxicity; 5) Disease activity; 6) Renal outcomes; 7) ANCA titer changes; 8) Healthcare resource utilization; 9) Healthcare costs (analysis from MGH only); 10) Adverse events attributed to avacopan; 11) Infection; 12) Relapse (defined as a return (after prior improvement) of vasculitis activity on the basis of at least one major BVAS/WG item, at least three minor BVAS v3 items, or one or two minor BVAS v3 items for at least two consecutive clinical visits); 13) Mortality; 14) Patient reported outcome measures (RAPID-3, mHAQ, PHQ-8, GAD-7, and PROMIS)

Covariates include: 1) Demographic features (e.g., age, sex, race/ethnicity); 2) GPA/MPA features (e.g., BVAS v3, organ involvement, new or relapsing disease); 3) Comorbidities at index date (e.g., hypertension, hyperlipidemia, Charlson Comorbidity Index)

All exposures, outcomes, and covariates are routinely collected via clinically-collected data at Mass General Brigham, as stored in the electronic health record and/or electronic data warehouse.

### **Study Sample Size**

- There are 133 patients identified through January 2024 from within the Mass General Brigham system who have been prescribed avacopan and 112 have initiated avacopan. Additionally, since December 1, 2021, there are 60 patients diagnosed with GPA/MPA in the MGB system who were not prescribed avacopan. Among those who have initiated avacopan, there have been 23 relapses. Glucocorticoid exposure has varied but the majority of patients have discontinued glucocorticoids within 2 months of avacopan initiation. There are only 2 patients in this cohort with missing status regarding avacopan initiation.

### **Data Analysis**

- The primary and secondary outcomes will be analyzed using a descriptive approach. Summary statistics for continuous variables, including the number of patients, mean, standard deviation (SD), median, Q1, Q3, minimum and

maximum, will be calculated after excluding missing/unknown values. For categorical variables, the frequency and percentage will be provided, and a category of “missing/unknown” will be included. Cumulative incidence will be used to describe the occurrence of key outcomes, including glucocorticoid toxicities, infections, and relapse. Given the variable follow-up time, healthcare resource utilization (HCRU) and costs will be presented as per patient per month (PPPM) metrics. Time to event outcomes (e.g., time to discontinuation of glucocorticoids) will be calculated using Kaplan-Meier analysis and median follow-up time (interquartile range [IQR]) will be reported.

- Among avacopan users, we will consider analyses evaluating time to events (e.g., glucocorticoid discontinuation, relapse) with adjustment for covariates. We will consider Cox proportional hazard regression models or other methods for time to event analyses and incorporate covariates, considering the number of observed outcomes. Restricted mean survival time will be used to describe time free from glucocorticoid exposure during follow-up.
- Among avacopan users, exploratory analysis of the association of glucocorticoid exposure with the risk of relapse will be assessed using an emulated target trial framework with a clone, censor, weighting approach. Cluster analysis will be used to explore patterns of glucocorticoid prescribing for patients using avacopan. Cox proportional hazards models will be used to evaluate factors associated with the risk of relapse and factors associated with glucocorticoid discontinuation.

CCI

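### Dropping missing values makes visit averages such as eGFR cover different patients at baseline and at Months 6 and 12, so an average can improve with no patient improving

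*Protocol*

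**What the plan says.** The Data Analysis section of the protocol abstract opens with "The primary and secondary outcomes will be analyzed using a descriptive approach". For continuous variables it lists the number of patients, mean, SD, median, quartiles and range, and says these "will be calculated after excluding missing/unknown values". Categorical variables are treated differently: "a category of “missing/unknown” will be included".

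The Follow-up section sets the visits: "Analysis 3: Month 1, 3, 6, and 12 outcomes among patients who initiate avacopan". The endpoint table, under the primary objective on outcomes, includes "Renal parameters (estimated glomerular filtration rate [eGFR], proteinuria, hematuria)", a daily glucocorticoid dose and the metabolic domain of the Glucocorticoid Toxicity Index (GTI-MD). None of these three is worded there as a change. A1c, BMI and lipids are.

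Under Clinical Outcomes, death and loss to follow-up appear as end dates for time-to-event measures: "Date of death (for time from initiation to death)" and "Date of loss to follow-up (for time from initiation to outcomes of interest)". The visible text does not say how either is handled when a continuous value is summarised at a visit.

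Study Population or Data Resource ends data collection in April 2024. Study Sample Size counts patients identified through January 2024, of whom 133 "have been prescribed avacopan and 112 have initiated avacopan".

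**The concern.** Analysis 3 has no comparator, so a reader of the renal table will look from the baseline column to the Month 12 column. Under the stated rule those columns need not contain the same patients. Absence has two kinds of cause.

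- **Calendar.** With data ending in April 2024, a patient who started after about April 2023 cannot have a Month 12 value, and one who started after about October 2023 cannot have a Month 6 value. Initiators were still being counted through January 2024.
- **Death, loss or no measurement.** The values come from routine care, so absence may be related to how ill the patient was.

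If the second group had worse kidney function, removing them raises the later average even though nobody's eGFR rose. The reported number of patients shows that some left. It does not show who they were, why they left, or what their baseline values were.

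**Working it through.** The protocol gives no attrition rate, eGFR mean or effect size, so there is no figure of its own to reproduce. The check is how far an available-case mean moves when every patient stays exactly the same.

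**Inputs.** n = 112 initiators (Study Sample Size). Assumed: k patients absent at the visit, with a mean eGFR G units below the whole-cohort mean.

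**Formula.** Let the cohort mean be m. The remaining patients have mean (n·m − k·(m − G))/(n − k) = m + G·k/(n − k). The apparent gain is therefore G·k/(n − k), whatever m is.

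| Assumed loss | k | Remaining | G = 10 | G = 20 |
|---|---|---|---|---|
| 5% | 6 | 106 | 60/106 = 0.6 | 120/106 = 1.1 |
| 10% | 11 | 101 | 110/101 = 1.1 | 220/101 = 2.2 |
| 20% | 22 | 90 | 220/90 = 2.4 | 440/90 = 4.9 |
| 30% | 34 | 78 | 340/78 = 4.4 | 680/78 = 8.7 |

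If absence is unrelated to eGFR, G is 0 on average and so is the expected shift.

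**Simulation check.** I took 112 fixed eGFR values (normal quantiles centred at 50, SD 25, limited to 5–120; mean 50.3). The chance of leaving was proportional to exp(−eGFR/25), with 2,000 repeats. The mean apparent gain was 1.1, 2.1, 4.3 and 7.0 at 5, 10, 20 and 30% loss. If every patient truly lost 2 units, the apparent change was −0.9, +0.1, +2.3 and +5.0.

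**Glucocorticoid dose.** If the leavers took 5 mg/day more than the cohort mean (assumed), the mean dose falls by 5·k/(n − k): 0.3, 0.5, 1.2 and 2.2 mg/day at the same four loss rates. This applies to a mean. The listed endpoint is a median, for which the shift may be smaller.

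**Same-patient comparison.** Take an assumed cohort mean of 50, G = 20 and k = 22. The 90 remaining patients have a baseline mean of (112 × 50 − 22 × 30)/90 = 4,940/90 = 54.9. With no change in anyone, their Month 12 mean is also 54.9. Set against 50, that looks like a gain of 4.9. Set against their own baseline, the change is 0.

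**The case against.** The strongest objection is that excluding missing values is the ordinary default for descriptive tables. On this view, paired changes and disposition rows belong in an SAP that is not shown, and much of the protocol beyond the abstract is redacted. The abbreviation list names the National Death Index and the United States Renal Data System, so ascertainment of death and kidney failure may be described in text we cannot see. This stands as a caution. However, the exclusion rule is written into the protocol, so the point does not rest on silence.

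A reader might infer that all renal, glucocorticoid and toxicity results are biased in a favourable direction. The documents do not support that:

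- A1c, BMI and lipids are listed as changes, and the Variables section lists ANCA titers as changes. A paired change cannot show mean improvement if no patient improves.
- Toxicity occurrence uses cumulative incidence. The abbreviations for GTI-MD include an improvement score and a worsening score, whose names suggest within-patient change.
- Glucocorticoid discontinuation uses Kaplan-Meier and restricted mean survival time. Most patients are reported to have stopped glucocorticoids within 2 months, so a later median dose may be near zero whoever leaves.
- The two remission outcomes are proportions, and missing status stays visible in categorical summaries.
- Mortality is a separate outcome.

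A reader might also infer that unequal follow-up is dealt with only for utilization and cost. The time-to-event methods just listed contradict that. The gap is confined to continuous values at visits.

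Finally, no passage says that a full-cohort baseline mean will be set against a Month 12 mean as the renal result. The risk lies in what the stated rule permits.

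**Conclusion.** The point holds in narrow form. It applies chiefly to eGFR, and to daily glucocorticoid dose and the GTI-MD score only if their levels are compared across visits. Given the data cut, the baseline and Month 12 summaries will describe different patients unless no initiator started after about April 2023.

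Whether this biases the result, and by how much, cannot be known from the protocol. On assumed gaps of 10 to 20 eGFR units, the artefact is small at 5% loss (0.6 to 1.1) and material at 20% (2.4 to 4.9). A favourable direction requires that those absent through death or loss had worse values, which is plausible but not documented. Treating a death as a missing value is itself an inference: a dead patient has no later measurement, and no other rule is visible.

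The correction is worth making because it is cheap and removes the composition artefact whatever the attrition turns out to be.

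**What to change.** For each continuous outcome reported at Months 1, 3, 6 and 12, state that the summary will be the within-patient change in patients with both a baseline and a visit value, shown with the baseline mean of that same subset.

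Beside it, give the numbers who:

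- died;
- have kidney failure;
- were lost to follow-up;
- had not yet reached the visit at the data cut;
- were in follow-up without a measurement.

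An ordered eGFR summary with death and kidney failure as the worst categories would keep those patients in the denominator. It is an optional sensitivity summary, not a needed correction.

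The cost is analysis wording and extra table rows. Dates of death and loss are already to be collected; kidney-failure status needs confirming as available. The renal summary may look less favourable. The paired change still describes only patients who remain, which is why the counts must stand next to it.

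### Kaplan-Meier is assigned to non-fatal time-to-event outcomes with no stated role for death; the resulting overstatement is probably small, and cheap to avoid

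*Protocol*

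**What the plan says.** Two sentences in the protocol's Data Analysis section name an estimator for event outcomes among avacopan users.

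- "Cumulative incidence will be used to describe the occurrence of key outcomes", with relapse, infections and glucocorticoid toxicities given as examples. No estimator is named.
- "Time to event outcomes (e.g., time to discontinuation of glucocorticoids) will be calculated using Kaplan-Meier analysis".

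The follow-up lists show which outcomes are times from initiation. Under Treatment Outcomes these are avacopan discontinuation and glucocorticoid discontinuation. Under Clinical Outcomes the list includes "Date of relapse (any and stratified by major or minor), (for time from initiation to relapse") and adverse events. Death is listed as "Date of death (for time from initiation to death"), that is, for its own analysis. The two dates listed for outcomes of interest in general are end of follow-up and loss to follow-up.

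For covariate-adjusted work the plan is looser: "We will consider Cox proportional hazard regression models or other methods for time to event analyses". The visible text nowhere says whether a death ends another outcome's follow-up as censoring or as a competing event.

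**The concern.** A patient who dies can no longer relapse, have an infection or stop glucocorticoids. Kaplan-Meier with deaths censored treats that patient as still able to have the event later, with the same hazard as those who remain. One minus the curve then estimates a probability in a world without death. It is never below the proportion of patients who actually have the event, and it exceeds that proportion once deaths occur first.

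The direction of the error differs by outcome. Glucocorticoid discontinuation is a favourable event, so success is overstated. For relapse and adverse events, risk is overstated.

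Relapse also falls under both sentences. It is named under cumulative incidence, and it is listed as a time from initiation, which the next method sentence sends to Kaplan-Meier. If cumulative incidence means the competing-risk estimator, the report could carry two relapse probabilities that do not match. The study is primarily descriptive, so such estimates are its main product, and relapse and glucocorticoid discontinuation are the subject of its secondary objectives.

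**Working it through.** The protocol gives no event-probability estimate or death rate, so there is no figure of its own to reproduce. The check only sizes the gap.

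**Inputs from the protocol (Study Sample Size)**
- Initiators: 112 ("who have been prescribed avacopan and 112 have initiated avacopan").
- Relapses: "Among those who have initiated avacopan, there have been 23 relapses". Crude proportion 23/112 = 20.5%.
- Most patients stopped glucocorticoids within 2 months of starting avacopan.

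**Assumptions**
- Constant hazards from day 0. This is a simplification, since relapse is assessed only after Month 1.
- The 23 relapses are 23 patients.
- Mean follow-up of 0.75, 1.0 or 1.25 years.
- Median time to glucocorticoid discontinuation of 2 months.
- Annual mortality of 1%, 2%, 5% or 10%.

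**Formulas**
- Relapse hazard: h = −ln(1 − 23/112) / mean follow-up. With 1.0 year, h = 0.230 per year.
- Glucocorticoid discontinuation hazard: h = ln 2 / (2/12) = 4.16 per year.
- Death hazard: d = −ln(1 − annual mortality). At 5%, d = 0.0513.
- One minus Kaplan-Meier, deaths censored: 1 − exp(−h·t).
- Cumulative incidence with death competing: h/(h+d) × [1 − exp(−(h+d)·t)].

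**Worked case: relapse, Month 24, mean follow-up 1.0 year, 5% mortality**
- One minus Kaplan-Meier: 1 − exp(−0.460) = 36.85%.
- Cumulative incidence: 0.230/0.281 × [1 − exp(−0.562)] = 35.16%.
- Gap: 1.69 points.

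**Gap in percentage points by assumed annual mortality**

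| Outcome and time | 1% | 2% | 5% | 10% |
|---|---|---|---|---|
| Relapse, Month 12 (mean follow-up 1.0 year) | 0.10 | 0.20 | 0.50 | 1.01 |
| Relapse, Month 24 (mean follow-up 1.0 year) | 0.34 | 0.68 | 1.69 | 3.36 |
| Glucocorticoid discontinuation, Month 6 | 0.15 | 0.30 | 0.75 | 1.54 |
| Glucocorticoid discontinuation, Month 12 | 0.22 | 0.44 | 1.12 | 2.28 |
| Glucocorticoid discontinuation, Month 24 | 0.24 | 0.48 | 1.22 | 2.47 |

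Across all three follow-up assumptions, the relapse gap runs from 0.08 to 1.28 points at Month 12 and from 0.29 to 4.06 at Month 24. Restricted to 1% to 5% mortality, the upper ends are 0.63 and 2.05 points.

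**Cross-check with another hazard.** Assume uniform entry over 26 months and solve 1 − (1 − exp(−26h))/(26h) = 23/112. This gives h = 0.0184 per month. At Month 24, one minus Kaplan-Meier is 35.7%, against 34.1% with 5% mortality and about 32.4% with 10%. The gaps of about 1.6 and 3.3 points agree with the table.

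**Scale.** The standard error of 23/112 is √(0.205 × 0.795/112) = 3.8 points, with a 95% confidence interval of about 13% to 28%. Under uniform entry over 26 months and data through April 2024, only about 5/26 × 112 ≈ 22 initiators could have 24 months of observation, before any relapse, death or loss.

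**The case against.** The strongest reply is that the protocol never says relapse, infection and glucocorticoid toxicity will be estimated with death ignored. They are assigned to cumulative incidence, which is also the usual name of the competing-risk estimator. The visible text is an abstract, the text after it is redacted, and the analysis plan is not shown. Handling of death could sit in either place. This stands for those three outcomes: a reader might infer that the plan censors deaths there, but that would be inference from silence. It does not remove the point where Kaplan-Meier is the stated method. That is explicit for glucocorticoid discontinuation and follows for the other outcomes listed as times from initiation.

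A reader might also infer that the problem begins after Month 12. It does not. For relapse the gap builds gradually from time zero. For glucocorticoid discontinuation most of it arises early and hardly grows after Month 12. The planned assessment times are Months 1, 3, 6 and 12, and use beyond 12 months is only an exploratory objective, so the larger Month 24 figures fall where data are thinnest.

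The size also depends on a mortality the document does not give. At 1% to 2% per year, with mean follow-up of 1.0 year, the relapse gap is 0.1 to 0.2 points at Month 12 and 0.3 to 0.7 at Month 24. That stands too, and it is why the point is minor. The bias does, however, have a known direction, and more patients would not reduce it.

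**Conclusion.** The point holds as a minor one. The plan names Kaplan-Meier for time-to-event outcomes and gives death no role except as its own outcome. With deaths censored, the reported probabilities of non-fatal events will be at or above the actual ones, and the relapse figure may conflict with a competing-risk cumulative incidence.

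The sizes given rest on assumed mortality of 1% to 10% per year, constant hazards and an assumed follow-up. Only at the top of the mortality range and at late times does the relapse gap come near the 3.8-point standard error of the crude relapse proportion.

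A reader might infer that the main results are biased. The documents do not support that: the two primary remission endpoints at Months 6 and 12 are proportions, not Kaplan-Meier estimates, and outcomes are not hypothesis-tested.

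**What to change.** In Data Analysis, replace Kaplan-Meier for the non-fatal time-to-event outcomes (glucocorticoid discontinuation, avacopan discontinuation, relapse, infection and glucocorticoid toxicity) with the Aalen-Johansen cumulative incidence, with death as competing event. Say that this is what cumulative incidence means throughout, so that relapse has one estimator. Report 95% confidence intervals at Months 6 and 12, and at later times only where enough patients remain at risk. Keep Kaplan-Meier for death.

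The cost is a few words and slightly more analysis work with standard software. No new data are needed, because death dates are already to be collected. Reported event probabilities will be slightly lower.
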